14.1.4 Anticipated/Unanticipated Serious Adverse Device Effect (ASADE/USADE)

An USADE is a serious ADE that meets any of the above definitions but is also considered, by the Investigator, to be caused by or related to the IP, not previously identified in nature, severity or degree in the IFU.

An Anticipated Serious Adverse Device Effect (ASADE) is a serious ADE that does not meet the criteria for a USADE.

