5.3 SAFETY CONSIDERATIONS

The PEEK suture anchor family, which include the following products: DYNOMITE°, SPYROMITE°, RAPTORMITE° and FOOTPRINT° ULTRA PK SL, are intended for reattachment of soft tissue to bone fixation in the joint extremities such as elbow, wrist, hand, foot and ankle. Representative language of the contraindications and potential adverse events can be found in the Instructions for Use (IFU) for each product.

Table 2: Instructions for Use Reference Numbers

PEEK Suture Anchor	IFU
DYNOMITE°	01/2017 10600401 Rev. D
SPYROMITE°, RAPTORMITE°	01/2017 10600400 Rev. D
FOOTPRINT° ULTRA PK SL	03/2017 10600402 Rev. E
	2017 10601001 REV. B

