14.1 DEFINITIONS

The categories of adverse events are shown in table 5. The definitions for each of these categories are given in the subsequent sections (see reference within the table).

CONFIDENTIAL AND PROPRIETARY

This document contains information that is confidential and proprietary to Smith & Nephew PLC and Smith & Nephew, Inc. and is intended for use only by Smith & Nephew and its manufacturer. It shall not be reproduced or copied in whole or in part, nor shall the contents be disclosed by any means without prior written permission from Smith & Nephew, nor shall anyone make any use of it that is contrary to the expressed or implied wishes of Smith & Nephew.

Study Protocol—Device	
Safety and Performance of PEEK Anchors (DYNOMITE°, SPYROMITE°, RAPTORMITE°, FOOTPRINT° ULTRA PK SL) in Extremities	Number: 2018.15.SMD.PEEK.RET.EXT
	Version: 2.0 05Dec2018
	Page: Page 32 of 54

Table 5: Categories of Adverse Event

	NOT DEVICE-RELATED	DEVICE- OR PROCEDURE-RELATED	
NON-SERIOUS	ADVERSE EVENT (AE) (SEE 14.1.1)	ADVERSE DEVICE EFFECT (ADE) (SEE 14.1.2)	
SERIOUS	SERIOUS ADVERSE EVENT (SAE) (SEE 14.1.3)	SERIOUS ADVERSE DEVICE EFFECT (SADE) (SEE 14.1.3)	
		ANTICIPATED	UNANTICIPATED
		ANTICIPATED SERIOUS ADVERSE DEVICE EFFECT (ASADE) (SEE 14.1.4)	UNANTICIPATED SERIOUS ADVERSE DEVICE EFFECT (USADE) (SEE 14.1.4)

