14.1.2 Adverse Device Effect (ADE)

An ADE is an adverse event that, in the opinion of the Investigator, is related to the IP or the procedure.

CONFIDENTIAL AND PROPRIETARY

This document contains information that is confidential and proprietary to Smith & Nephew PLC and Smith & Nephew, Inc. and is intended for use only by Smith & Nephew and its manufacturer. It shall not be reproduced or copied in whole or in part, nor shall the contents be disclosed by any means without prior written permission from Smith & Nephew, nor shall anyone make any use of it that is contrary to the expressed or implied wishes of Smith & Nephew.

Study Protocol—Device	
Safety and Performance of PEEK Anchors (DYNOMITE°, SPYROMITE°, RAPTORMITE°, FOOTPRINT° ULTRA PK SL) in Extremities	Number: 2018.15.SMD.PEEK.RET.EXT
	Version: 2.0 05Dec2018
	Page: Page 33 of 54

Not Related - An AE is considered to be not related to the use of an IP or the procedure when the effect is DEFINITELY UNRELATED or UNLIKELY to have any relationship to the use of the IP or the procedure;

Related – An AE is considered to be related to the use of an IP or the procedure when there is a POSSIBLE, PROBABLE, or DEFINITE relationship between the AE and the use of the IP or the procedure.

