14.1.3 Serious Adverse Events (SAE) and Serious Adverse Device Effects (SADE)

An AE or ADE is considered a SAE or SADE if, in the view of either the Investigator or the Sponsor, it:

- Results in death.
- Is life-threatening (*NOTE:* The term “life-threatening” in the definition of “serious” refers to an event/reaction in which the subject was at risk of death at the time of the event/reaction; it does not refer to an event/reaction which hypothetically might have caused death if it were more severe).
- Requires in subject hospitalization or results in prolongation of existing hospitalization.
- Results in persistent or significant incapacity or substantial disruption of the ability to conduct normal life functions.
- Is a congenital anomaly/birth defect.
- Is a medically important event or reaction.

Medical and scientific judgment should be exercised in deciding whether other situations should be considered serious such as important medical events that might not be immediately life-threatening or result in death or hospitalization but might jeopardize the subject or might require

CONFIDENTIAL AND PROPRIETARY

This document contains information that is confidential and proprietary to Smith & Nephew PLC and Smith & Nephew, Inc. and is intended for use only by Smith & Nephew and its manufacturer. It shall not be reproduced or copied in whole or in part, nor shall the contents be disclosed by any means without prior written permission from Smith & Nephew, nor shall anyone make any use of it that is contrary to the expressed or implied wishes of Smith & Nephew.

Study Protocol—Device	
Safety and Performance of PEEK Anchors (DYNOMITE°, SPYROMITE°, RAPTORMITE°, FOOTPRINT° ULTRA PK SL) in Extremities	Number: 2018.15.SMD.PEEK.RET.EXT
	Version: 2.0 05Dec2018
	Page: Page 34 of 54

intervention to prevent one of the other outcomes listed in the definition above. Examples of such events are intensive treatment in an emergency room or at home for allergic bronchospasm, blood dyscrasias, or convulsions that do not result in hospitalization; or development of drug dependency or drug abuse.

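### A serious event related only to the procedure and absent from the IFU is labelled anticipated, because ASADE is the remainder after an IP-only USADE definition

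*Combined protocol and SAP*

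**What the plan says.** Section 14.1.2 sets the scope of a device effect: "An ADE is an adverse event that, in the opinion of the Investigator, is related to the IP or the procedure". An event counts as related "when there is a POSSIBLE, PROBABLE, or DEFINITE relationship between the AE and the use of the IP or the procedure". Section 14.1.3 adds seriousness, with no further relatedness test: "An AE or ADE is considered a SAE or SADE if, in the view of either the Investigator or the Sponsor, it" meets one of the listed criteria.

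Table 5 in 14.1 places ADE, SADE, ASADE and USADE under the heading "DEVICE- OR PROCEDURE-RELATED" and divides the serious cell into two parts only, anticipated and unanticipated, both referred to 14.1.4.

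Section 14.1.4 says that a USADE is a serious ADE that the Investigator considers "to be caused by or related to the IP, not previously identified in nature, severity or degree in the IFU". It then closes the classification: "An Anticipated Serious Adverse Device Effect (ASADE) is a serious ADE that does not meet the criteria for a USADE".

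Section 12.4 lists ASADEs and USADEs separately in the overall AE table and summarizes each classification by event.

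**The concern.** The two definitions in 14.1.4 rest on a narrower relatedness basis than the category they divide. ADE and SADE cover the IP or the procedure; USADE covers the IP only. ASADE takes whatever is left and has no IFU test of its own, so it receives events for which nobody has established that they were anticipated.

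What is at stake is how a safety table is read. Safety is part of the primary objective (7.1), and the synopsis says the study is meant to address clinical data gaps for device regulation. A reader of the 12.4 tables would take an ASADE entry as something the IFU had already identified. For an unlisted serious procedural event that reading would be false. The by-event summary would still show the event term, but under the reassuring label.

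**Working it through.** No figure in the plan is involved, so the check consists of applying the definitions to every kind of serious ADE.

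**Inputs**
- ADE: related to the IP or the procedure (14.1.2).
- SADE: an ADE that meets a seriousness criterion (14.1.3).
- USADE: a SADE that is related to the IP and not identified in the IFU (14.1.4).
- ASADE: a SADE that is not a USADE (14.1.4).

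**Combinations.** An ADE has three relatedness patterns (IP only, procedure only, both) and two IFU states (identified, not identified): 3 × 2 = 6 cells.

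| Related to IP | Related to procedure | Identified in IFU | Label under 14.1.4 | Label agrees with IFU status |
|---|---|---|---|---|
| yes | no | no | USADE | yes |
| yes | no | yes | ASADE | yes |
| yes | yes | no | USADE | yes |
| yes | yes | yes | ASADE | yes |
| no | yes | yes | ASADE | yes |
| no | yes | **no** | **ASADE** | **no** |

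ASADE holds 4 cells, 3 in the IFU and 1 not. USADE holds 2. Of the 3 cells not in the IFU, 2 are USADE and 1 is ASADE. None of the 4 IP-related cells is mislabelled; the single mismatch is the procedure-only, unlisted cell.

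**Can IP be read to include the procedure?** No. Section 14.1.2 names the two as alternatives, 14.2 has the Investigator assess relationship to each, and 14.3.1 also lists them as alternatives.

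**Does other text correct it?** Not in the text available. The opening of Section 14 in fact includes USADE among events related to the implant or the procedure, which is broader than 14.1.4 and should be reconciled with it. Figure 1 in 14.2 is not shown, so its handling of this case could not be checked.

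**After the change**
- USADE widened to IP or procedure, ASADE defined by the IFU: USADE 3 cells (all unlisted), ASADE 3 (all listed), 0 of 6 mislabelled.
- USADE kept IP-specific, with a separate label for unlisted procedure-only events: USADE 2, ASADE 3, separate label 1, 0 of 6 mislabelled.

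**The case against.** The strongest reply is that 14.1.4 never says an ASADE is an event listed in the IFU. It defines the category as a remainder, the rule gives exactly one answer for every serious ADE, and a count produced under it would be correct by its own terms. On this view the complaint is only that anticipated is a poor name for a residual group. That is fair as to the count, but the name is what the reader of the table sees, and the protocol offers no basis other than the IFU for calling an event anticipated. Section 5.3 points to the same source: "Representative language of the contraindications and potential adverse events can be found in the Instructions for Use (IFU) for each product".

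A second reply is that the cell is narrow. This stands. Because a possible relationship counts as related, an unlisted event even possibly linked to the anchor remains a USADE. The event must be serious, unlisted, judged unlikely or definitely not related to the anchor, and yet related to the operation.

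Third, the consequences are contained. This also stands. Section 14.2 sends all ADEs and SAEs to the Sponsor within 24 hours and has all of them medically reviewed, whatever their label. Section 12.4 also tabulates AEs by relatedness to the device, which gives a reader some protection.

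Fourth, Table 5 has a left-hand column for events not related to the device, and a procedure-only event fits that heading literally. The headings do overlap, but 14.1.2 settles the matter by making such an event an ADE.

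Finally, widening USADE would attach a device-effect label to events judged unrelated to the device. The protocol already does this when it calls procedure-only events ADEs, and the separate-label option avoids extending it.

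**Conclusion.** The concern holds as a minor fault in the definitions. As written, one of six kinds of serious ADE, the procedure-only event not identified in the IFU, is reported as anticipated. The one-in-six figure is an unweighted count of categories and says nothing about frequency: the documents give neither event rates nor the contents of the IFUs, so the number of affected events is unknown and may be zero.

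The primary and secondary endpoints, the safety endpoints named in 10.2.3, SADE totals and IP-related USADE counts do not change. The conclusion rests on the wording of 14.1.2 to 14.1.4 and Table 5, and assumes that Figure 1, which is not available, does not override them.

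**What to change.** In 14.1.4, define ASADE positively as a serious ADE whose nature, severity and degree are identified in the IFU. Then choose one of two ways to deal with the remaining cell:

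1. Put USADE on the same relatedness basis as 14.1.2 and Table 5, that is, the IP or the procedure.
2. Keep USADE specific to the IP, and report unlisted procedure-only serious events under their own label in Table 5 and in the 12.4 tables.

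Whichever is chosen, bring the opening of Section 14 into line, check Figure 1 against it, and carry the classification into the SAP, which Section 12 says will be finalized before database lock.

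The cost is one or two sentences in 14.1.4. No extra data are needed, because 14.2 already has the Investigator assess relationship to device and to procedure. The downside is possibly a few more events labelled unanticipated under the first option, or one more label and table row under the second.

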14.1.5 Severity

The severity of every AE will be assessed by the Investigator or medically qualified site staff to whom the responsibility has been delegated and documented on the delegation of authority log. AEs should be classified as mild, moderate, or severe, regardless of whether or not the AEs are considered to be serious or non-serious. The classification should be based on the following definitions:

- Mild -** An event is mild if the subject is aware of, but can easily tolerate the sign or symptom;
- Moderate -** An event is moderate if the sign or symptom results in discomfort significant enough to cause interference with the subject’s usual activities;

CONFIDENTIAL AND PROPRIETARY

This document contains information that is confidential and proprietary to Smith & Nephew PLC and Smith & Nephew, Inc. and is intended for use only by Smith & Nephew and its manufacturer. It shall not be reproduced or copied in whole or in part, nor shall the contents be disclosed by any means without prior written permission from Smith & Nephew, nor shall anyone make any use of it that is contrary to the expressed or implied wishes of Smith & Nephew.

Study Protocol—Device	
Safety and Performance of PEEK Anchors (DYNOMITE [®] , SPYROMITE [®] , RAPTORMITE [®] , FOOTPRINT [®] ULTRA PK SL) in Extremities	Number: 2018.15.SMD.PEEK.RET.EXT
	Version: 2.0 05Dec2018
	Page: Page 35 of 54

Severe - An event is severe if the sign or symptom is incapacitating and results in the subject’s inability to work or engage in their usual activities.

14.1.6 Device Deficiency

A Device Deficiency (DevD) is an inadequacy of a medical device with respect to its identity, quality, durability, reliability, safety or performance. DevD includes malfunctions, use errors and inadequate labelling.

14.2 REPORTING PROCEDURES

AEs of any kind and DevDs will be recorded in the applicable CRF and source notes. The Investigator will evaluate all AEs for relationship to the device and procedure, if applicable, seriousness, and severity. ADEs, SAEs, and DevDs will be submitted/entered into the CRF and reported to the Sponsor within 24 hours of the Investigator being informed about the event (Figure 1). For ADEs and DevDs, details of the product/procedure related to the event will be recorded in the CRF within 24 hours of the retrospective chart review.

All SAEs and ADEs will be reviewed by a medically qualified person appointed by the Sponsor to determine which, if any, meet criteria for expedited reporting to the regulatory authorities. The Investigator will inform the IRB of AEs according to the IRB requirements.

Depending on the nature of the AE, the Sponsor may request copies of the subject’s medical records, imaging, operative notes, as well as results of any relevant laboratory tests performed or other documentation related to the AE. If the subject was hospitalized, a copy of the discharge summary may be requested by the Sponsor and should be forwarded as soon as it becomes

[figure not shown]
CONFIDENTIAL AND PROPRIETARY

This document contains information that is confidential and proprietary to Smith & Nephew PLC and Smith & Nephew, Inc. and is intended for use only by Smith & Nephew and its manufacturer. It shall not be reproduced or copied in whole or in part, nor shall the contents be disclosed by any means without prior written permission from Smith & Nephew, nor shall anyone make any use of it that is contrary to the expressed or implied wishes of Smith & Nephew.

Study Protocol—Device	
Safety and Performance of PEEK Anchors (DYNAMITE°, SPYROMITE°, RAPTORMITE°, FOOTPRINT° ULTRA PK SL) in Extremities	Number: 2018.15.SMD.PEEK.RET.EXT
	Version: 2.0 05Dec2018
	Page: Page 36 of 54

available. In certain cases, the Sponsor also may request a letter from the Investigator that summarizes the events related to the case.

Figure 1: Evaluation and Reporting of AE and DevD

Reference the Investigator Site File Sponsor Contact Information Sheet to report SAEs, unanticipated ADEs and SADEs, anticipated SADEs, and DevDs.

CONFIDENTIAL AND PROPRIETARY

14.3 FOLLOW-UP OF SUBJECTS WITH ADVERSE EVENTS

For subjects who are experiencing an ongoing unresolved AE at the time of their study completion or early discontinuation from the study, it is recommended that the investigator follow-up with the patient per standard clinical practice.

Any additional data must be documented and available to the Sponsor who will determine whether the data needs to be documented within the CRF/Clinical Study Report.

14.3.1 Ongoing Adverse Events at Study Discontinuation

Adverse events which are **related** to a study procedure or IP and are ongoing at end of subject's participation: The event should be followed until it is either resolved or until the event has become chronic and is not expected to further improve based on Investigator's review of the event.

Adverse events which are **not related** to a study procedure or IP and are ongoing at end of subject's participation should be followed for 30 days after discontinuation or if the AE is resolved, whichever is sooner.

At the time of data analysis (e.g. interim or final), an evaluation of ongoing events should take place and be listed as ongoing in the safety table.

15. INVESTIGATOR OBLIGATIONS

The Principal Investigator (PI) will comply with the commitments outlined in the in the Statement of Investigator and with GCP, and all applicable regulatory requirements.

16. SPONSOR AND MONITOR RESPONSIBILITIES

The Sponsor will designate a monitor to conduct the appropriate site visits at the appropriate intervals. The clinical investigation will be monitored to ensure that: the rights and wellbeing of the

CONFIDENTIAL AND PROPRIETARY

This document contains information that is confidential and proprietary to Smith & Nephew PLC and Smith & Nephew, Inc. and is intended for use only by Smith & Nephew and its manufacturer. It shall not be reproduced or copied in whole or in part, nor shall the contents be disclosed by any means without prior written permission from Smith & Nephew, nor shall anyone make any use of it that is contrary to the expressed or implied wishes of Smith & Nephew.

Study Protocol—Device	
Safety and Performance of PEEK Anchors (DYNOMITE°, SPYROMITE°, RAPTORMITE°, FOOTPRINT° ULTRA PK SL) in Extremities	Number: 2018.15.SMD.PEEK.RET.EXT
	Version: 2.0 05Dec2018
	Page: Page 38 of 54

subjects are protected; the reported data are accurate, complete, and verifiable from the source documents; and the study is conducted in compliance with the currently approved protocol, with GCP regulations, and with applicable regulatory requirements.

Detailed monitoring requirements will be documented within the Clinical Monitoring Plan for this study.

16.1 SITE QUALIFICATION VISIT

A site qualification visit may be performed by the Sponsor or qualified person designated by the Sponsor prior to the execution of a clinical agreement to ensure that all Investigators have the appropriate training, staff, facilities, and resources to adequately conduct the study.

16.2 SITE INITIATION VISIT

A site initiation visit to provide training on the specifics of the study, site obligations and expectations of study conduct will be performed by the Sponsor or qualified person designated by the Sponsor following the execution of the Clinical Trial Agreement (CTA) and documented IRB/EC approval.

16.3 SPONSOR AUDITS AND REGULATORY INSPECTION

Quality Assurance auditors, whether an employee of the Sponsor or its designee, may evaluate study conduct at the study sites. These parties must have access to any and all study reports and source documentation, regardless of location and format.

CONFIDENTIAL AND PROPRIETARY

This document contains information that is confidential and proprietary to Smith & Nephew PLC and Smith & Nephew, Inc. and is intended for use only by Smith & Nephew and its manufacturer. It shall not be reproduced or copied in whole or in part, nor shall the contents be disclosed by any means without prior written permission from Smith & Nephew, nor shall anyone make any use of it that is contrary to the expressed or implied wishes of Smith & Nephew.

Study Protocol—Device	
Safety and Performance of PEEK Anchors (DYNOMITE[°], SPYROMITE[°], RAPTORMITE[°], FOOTPRINT[°] ULTRA PK SL) in Extremities	Number: 2018.15.SMD.PEEK.RET.EXT
	Version: 2.0 05Dec2018
	Page: Page 39 of 54

16.4 CLOSE-OUT VISIT

A study close-out visit will be performed by the Sponsor or designee to retrieve and account for all remaining clinical data and to resolve outstanding queries. During study close-out, the monitor will review investigator files to ensure required documents and records are on file, confirm the disposition of any other ancillary items used for the study, and review regulatory requirements regarding records retention and IRB/IEC reporting requirements.

17. PROTOCOL AMENDMENTS

Amendments should be made only in exceptional cases once the study has started. Protocol amendments must be approved by the protocol signatories prior to submission to the IRB. Protocol amendments need to be approved by the IRB and Regulatory Authority (ies), as applicable prior to implementation at the site.

18. CONFIDENTIALITY OF THE STUDY

The confidentiality of this study and associated documents is governed by the terms of the CTA.

19. STATEMENTS OF COMPLIANCE

This clinical study will be performed in compliance with the ethical principles of the Declaration of Helsinki; International Organization for Standardization (ISO) 14155: Clinical investigation of medical devices – Good Clinical Practice (GCP); and the International Council for Harmonisation (ICH)-E6.

This clinical study will not commence until the required approval/favorable opinion from the IRB or regulatory authority has been obtained. Any additional requirements imposed by the IRB or regulatory authority will be followed.

CONFIDENTIAL AND PROPRIETARY

This document contains information that is confidential and proprietary to Smith & Nephew PLC and Smith & Nephew, Inc. and is intended for use only by Smith & Nephew and its manufacturer. It shall not be reproduced or copied in whole or in part, nor shall the contents be disclosed by any means without prior written permission from Smith & Nephew, nor shall anyone make any use of it that is contrary to the expressed or implied wishes of Smith & Nephew.

Study Protocol—Device	
Safety and Performance of PEEK Anchors (DYNOMITE°, SPYROMITE°, RAPTORMITE°, FOOTPRINT° ULTRA PK SL) in Extremities	Number: 2018.15.SMD.PEEK.RET.EXT
	Version: 2.0 05Dec2018
	Page: Page 40 of 54

